9. ADVERSE EVENTS

9.1 GENERAL INFORMATION

An adverse event (AE) is any untoward medical occurrence in a patient administered a medicinal product and which does not necessarily have to have a causal relationship with this treatment. An adverse event can therefore be any unfavorable and unintended sign (for example, an abnormal laboratory finding), symptom, or disease temporally associated with the use of a medicinal product, whether or not considered related to this medicinal product.

Adverse drug reactions (ADR) are noxious and unintended responses to a medicinal product, meaning that a causal relationship between a medicinal product and an adverse event is at least a reasonable possibility. A reaction, in contrast to an event, is characterized by the fact that a causal relationship between the drug and the occurrence is suspected.

Adverse Event CRF must be used to document all adverse events that occur during the course of the study. For each recorded event, the CRF must include the event's onset and resolution date (if the event has resolved), the frequency and severity of the event, a summary of any action taken as a result of the event (both in regard to any treatment given and to any change in dosing with the test article), and an assessment of the event's relationship to the test article.

a Serious Adverse Events that are suspected to be related to the test article and are unexpected (not identified in the product-package insert), should be reported to IRB and to the manufacturer of the test article within 24 hrs of the investigator's knowledge as described below in section 10.4

9.2 Non-serious Adverse Events

A non-serious adverse event is defined as a change from baseline (pre-treatment) in a subject's medical health that is not life-threatening, does not require hospitalization, does not prolong a current hospitalization, and is not disabling.

9.3 SERIOUS ADVERSE EVENTS

A serious adverse event or reaction is any untoward medical occurrence that at any dose:

Results in death

- Is life-threatening (*NOTE*: The term "life-threatening" in the definition of "serious" refers to an event/reaction in which the patient was at risk of death at the time of the event/reaction; it does not refer to an event/ reaction which hypothetically might have caused death if it were more severe)
- Requires inpatient hospitalization or results in prolongation of existing hospitalization
- Results in persistent or significant disability/incapacity
- Is a congenital anomaly/birth defect
- Is a medically important event or reaction

Medical and scientific judgment should be exercised in deciding whether other situations should be considered serious such as important medical events that might not be immediately life-threatening or result in death or hospitalization but might jeopardize the patient or might require intervention to prevent one of the other outcomes listed in the definition above. Examples of such events are intensive treatment in an emergency room or at home for allergic bronchospasm, blood dyscrasias, or convulsions that do not result in hospitalization; or development of drug dependency or drug abuse.

9.4 REPORTING OF SERIOUS ADVERSE EVENTS

A Serious Adverse Event Form must be completed for all serious adverse events to the Institutional Review Board according to their requirements.

9.5 ADVERSE EVENT SEVERITY AND CAUSALITY ASSESSMENT

Events should be classified as mild, moderate, or severe, regardless of whether or not the events are considered to be serious or non-serious. The classification should be based on the following definitions:

- Mild An event is mild if the subject is aware of, but can easily tolerate the sign or symptom
- **Moderate** An event is moderate if the sign or symptom results in discomfort significant enough to cause interference with the subject's usual activities
- Severe An event is severe if the sign or symptom is incapacitating and results in the subject's inability to work or engage in their usual activities

In addition, the Principal Investigator will determine adverse event causality according to the following definitions and with due consideration to conditions and AE normally associated with the population under study:

- **Not Related** An event is considered to be not related to the use of the test article when the event is DEFINITELY UNRELATED or UNLIKELY to have any relationship to the use of the test article.
- Related An event is considered to be related to the use of the test article when there is a
 POSSIBLE, PROBABLE, or DEFINITE relationship between the adverse event and the use of
 the test article.

For example, a single occurrence of an event that is uncommon and known to be strongly associated with drug exposure (e.g., angioedema, hepatic injury, Stevens - Johnson syndrome) has a reasonable possibility of association with the test article. One or more occurrences of an event that is not commonly associated with drug exposure, but is otherwise uncommon in the population exposed to the test article, may have a reasonable possibility of association. Adverse events which are known to be common in the population under study would require additional evidence (e.g., strong temporal relationship, recurrence on re-challenge, unusual severity, and/or increasing frequency) before being considered possibly related.

Adverse events which are known to occur frequently in the population defined by this protocol include: burn wound infection, pain and itch of the burn wound, and contact dermatitis.

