2.2 RATIONALE

Outpatient management of partial thickness burns normally involves the application of an ointment, which may contain an antibiotic. Concerns about the promotion of antibiotic resistant staphylococci, combined with known risks of allergic hypersensitivity reactions to certain topical antibiotics, support the exploration of alternative treatments. Bacitracin ointment has been compared against white petrolatum in the management of post-procedural wounds among 922 patients with 1249 wounds (17). No significant difference was observed in infection rates (2% in the petrolatum group vs. 0.9% in the bacitracin group) or healing rates. No patients in the white petrolatum group developed allergic contact dermatitis compared with 4 patients (0.9%) in the bacitracin group. In a separate study of 142 patients, 147 Mohs micrographic surgery wounds on the ear were postoperatively treated with either gentamicin ointment or petrolatum. No significant differences were seen between treatments in the incidence of suppurative chondritis infections (4.76% in the gentamicin group; 6.67% in the petrolatum group), whereas there was a higher incidence of inflammatory chondritis in the gentamicin group (11.90% vs. 3.33% for petrolatum) (18). In the 1990s, the North American Contact Dermatitis Group (NACDG) listed bacitracin among the top 10 allergens, based on skin testing. Approximately 9% of bacitracin tests were positive.

. Bacitracin ointment is selected for this study because it is a standard treatment used by the Investigators, and is widely used in burn care. A significant cost difference exists between bacitracin and other ointments, such as Collagenase Santyl. The therapeutic intent for this study is to see if there is a cost reduction benefit as well as reduction in healing time for two standard of care treatment options for partial thickness burn wounds.

This trial does not include a rigorous evaluation of local infection, as quantitative bacteriology from biopsied tissue would be required, nor does it include a rigorous evaluation of hypersensitivity reactions, as de-challenge / re-challenge or measurement of specific humoral and cellular immune responses would be required. Instead, the appearance of the wound bed and periwound tissue will be evaluated, with

particular attention to the description of any rashes. Clinically diagnosed infections may be treated, but use of topical treatment will require that the subject exit the trial.

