6. STUDY DESIGN

6.1 STUDY DESIGN

This is an active comparator, parallel group study in which subjects with burns meeting the study criteria will be randomly assigned to outpatient treatment with Santyl or bacitracin in a 1:1 ratio. Subjects who appear eligible will be presented with the study, and consent / assent will be obtained prior to any study procedures being conducted. The safety variables include adverse events and, specifically, burn wound infection or allergic contact dermatitis during treatment. Efficacy variables include time to complete healing and scar appearance. Both the Investigators and the subjects will contribute to these evaluations.

Enrolled, randomized subjects will be prescribed with test article (Santyl or bacitracin) and burn wound dressing supplies sufficient to last until burn wound has healed. Scar assessments will occur at 3 months and 6 months post burn healing.

Recruitment bias will exist, as any subject with a known contact dermatitis to bacitracin will be excluded. This will artificially reduce the number of allergic contact rashes in the bacitracin group, but the effect on the primary endpoint is unlikely to be significant. Study Procedure

For a summary of the required procedures by visit, refer to Table 12: Study Plan.

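### Section 9.5 puts contact dermatitis under an extra-evidence rule for causality, although sections 2.2 and 6.1 treat it as a reaction to bacitracin and a named safety variable (minor)

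*Combined protocol and SAP*

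**What the plan says.** Section 9.5 sorts causality into two categories. An event is Not Related "when the event is DEFINITELY UNRELATED or UNLIKELY to have any relationship to the use of the test article". It is Related when there is a "POSSIBLE, PROBABLE, or DEFINITE relationship between the adverse event and the use of" the test article. There is no third category.

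The same section then sets a rule for background events: "Adverse events which are known to be common in the population under study would require additional evidence". It gives examples of that evidence and says what the evidence permits: "strong temporal relationship, recurrence on re-challenge, unusual severity, and/or increasing frequency) before being considered possibly related". The closing paragraph of 9.5 lists the events regarded as frequent in this population; they "include: burn wound infection, pain and itch of the burn wound, and contact dermatitis".

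Two other sections treat dermatitis differently. Section 2.2, reporting a comparison of bacitracin with white petrolatum in post-procedural wounds, says: "No patients in the white petrolatum group developed allergic contact dermatitis compared with 4 patients (0.9%) in the bacitracin group". Section 6.1 says: "The safety variables include adverse events and, specifically, burn wound infection or allergic contact dermatitis during treatment". Section 6.1 adds that excluding people with known bacitracin contact dermatitis will lower the number of allergic rashes in the bacitracin group.

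**The concern.** Section 2.2 gives hypersensitivity to topical antibiotics as one reason to look for alternatives, and section 6.1 expects allergic rash in the bacitracin group. The protocol therefore regards allergic contact dermatitis as something a test article can cause. Section 9.5 classes contact dermatitis as background and raises the bar before a test article may be suspected.

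Two outputs depend on the causality call. Section 7.2 summarises relationship to study medication by preferred term and treatment. Section 9.1 requires a 24-hour report to the IRB and the manufacturer for serious events that are both suspected to be related and unexpected. A rule that leans against attribution could thin out the first and, in a narrow case, delay or prevent the second.

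**Working it through.** The point rests on the text, and the plan states no figure to reproduce. The arithmetic at the end only gives the scale.

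**The causality rule**

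1. Related begins at possible; Not Related covers unlikely and definitely unrelated (9.5).
2. A common event needs additional evidence before it may be called possibly related (9.5).
3. Contact dermatitis is on the list of frequent events (9.5). The rule speaks of common events and the list of frequent ones. I read these as the same set, because the list directly follows the rule.
4. From 1 to 3, a contact dermatitis without additional evidence cannot be Related, and the only category left is Not Related. The documents do not state this default; it follows from the two-category scheme.

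**How hard the hurdle is**

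- The listed forms of evidence are examples joined by and/or, so one of them can be enough.
- Strong timing is available, but strong is not defined. Ointment is applied daily until healing, for up to six weeks (4.2), so nearly any local reaction in that period has some temporal association.
- Re-challenge is not part of this trial's evaluation (2.2).
- Increasing frequency would need several cases; see below.

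**What depends on the causality call**

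| Output | Depends on causality? |
|---|---|
| Treatment-emergent event frequencies by preferred term and arm (7.2) | No |
| Infection incidence by arm (7.1.1) | No |
| Rash recorded at weekly visits (6.5.1) | No |
| Serious-event form to the IRB (9.4) | No |
| Relationship summary by arm (7.2) | Yes |
| 24-hour report to IRB and manufacturer (9.1) | Yes, if serious and unexpected |

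**Scale**

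Inputs: 40 per group (section 8); 0.9% and the roughly 9% positive skin-test rate (both 2.2). Check on the 0.9%: if the 922 patients were split equally, 4/461 = 0.87%, which agrees. Both rates are assumptions here. The 0.9% comes from post-procedural wounds. The 9% is skin-test positivity rather than clinical incidence, and known hypersensitivity is excluded, so I take it as an upper value.

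Expected cases = 40p. P(at least 1) = 1 − (1 − p)^40. P(at least 2) = 1 − (1 − p)^40 − 40p(1 − p)^39.

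| p | Expected cases | P(at least 1) | P(at least 2) |
|---|---|---|---|
| 0.009 | 0.36 | 30% | 5% |
| 0.09 | 3.6 | 98% | 89% |

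At the lower rate the trial most likely sees no case on bacitracin, and a rising frequency could hardly be shown. At the upper rate there would be a handful of cases to classify.

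**The case against.** The best defence of 9.5 is that it guides judgement and does not dictate it. The Principal Investigator decides each case, the examples are not exhaustive, and a rash that appears promptly under a daily ointment may qualify on timing alone. The lack of re-challenge blocks nothing, since it is one example among four. All of this stands, so a reader who infers that every dermatitis will be filed as Not Related goes further than the text.

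Contact dermatitis is also a broader term than the allergic form named in 2.2 and 6.1. Both arms may receive Xeroform, paper tape and compression (6.2.1), which are possible non-drug causes. The evidence in 2.2 is four cases, and not in burns. With equal groups and no drug effect, all four would fall in the bacitracin arm with probability 0.5^4 = 6%. So 2.2 does not prove a drug effect. It does show that the protocol itself ties the event to bacitracin, and that is enough for the inconsistency.

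A reader might extend the point to burn wound infection, which 6.1 also names as a safety variable. The documents do not support that. Section 2.1 says second-degree burns can become infected, and 2.2 reports no significant difference in infection rates (2% on petrolatum, 0.9% on bacitracin). Infection is a reasonable background event, and 7.1.1 compares all observed infections by arm whatever their causality.

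Finally, a common evidence standard has some value in an unblinded trial, where attribution could otherwise differ by arm. That is a real cost of relaxing the rule for dermatitis.

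**Conclusion.** The inconsistency is real and minor. As written, 9.5 leans against attributing to a test article a reaction that 2.2 and 6.1 associate with one. It touches one descriptive summary in 7.2, on which no test is planned, and the 24-hour route in 9.1 for an event that is both serious and unexpected. Whether any local reaction would count as unexpected depends on the package inserts, which are not in the documents.

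Two larger consequences might be inferred, and neither holds. The first is that serious events would go unreported: 9.4 still sends a form to the IRB for every serious event, so only the 24-hour timing and the notice to the manufacturer are exposed. The second is that a safety signal would be erased. At 0.9% an arm expects 0.36 cases, so there is rarely a signal to lose. At 9% it expects 3.6, and reclassifying one or two would not typically leave none. The comparison of dermatitis counts between arms is intact in either case.

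The conclusion assumes that common and frequent in 9.5 mean the same set of events, and that allergic contact dermatitis falls under contact dermatitis. The case counts also assume that the section 2.2 rates carry over to burns.

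**What to change.** In section 9.5, delete contact dermatitis from the list of frequent events, or limit the entry to dermatitis with an identified non-drug cause such as tape or dressing. Add a sentence saying that periwound rash or allergic contact dermatitis arising under study ointment is judged for relatedness on its own facts, without the additional-evidence requirement.

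Leave burn wound infection on the list. No new table is needed, because section 7.2 already counts events by preferred term and arm without regard to causality.

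The cost is a change of protocol wording. A few more events will probably be called possibly related, by an investigator who knows the assigned treatment, so the relatedness summary should be read with that in mind.

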9.6 FOLLOW-UP OF SUBJECTS WITH ADVERSE EVENTS

For subjects who are experiencing ongoing unresolved adverse events at the time of their study completion or early discontinuation from the study, it is recommended that the Investigator schedule an appropriate follow-up visit in order to determine the outcome of the event.

10. INVESTIGATOR OBLIGATIONS

10.1 THE PRINCIPAL INVESTIGATOR WILL COMPLY WITH CURRENT GOOD CLINICAL PRACTICE (GCP), AND WITH ALL APPLICABLE REGULATORY REQUIREMENTS. .

12. STUDY PLAN

Table 1-: Study Procedures by Visit

	Visit 1	Visits 2-6	Visits 7-8				
Informed Consent	X						
Medical History/Demographics	X						
Concomitant Medications	X	X	X				
Inclusion/Exclusion	X						
Determine Fitzpatrick skin type	X						
Determine burn depth (laser Doppler)	X						
Pain and itch assessment	X	X	X				
Randomize	X						
Evaluate burn wound appearance	X	X					
Evaluate burn wound for closure	X	X*					
Apply daily treatment	X	X					
Photograph burn wound	X	X	X				
Cutometer measurement			X				
Subject scar assessment			X				
Vancouver Scar Scale			X				
Record Adverse Events	X	X	X				
• If wound closed, subject does not return until Visit 7.							

13. APPENDICES

13.1.1

13.1.2 Fitzpatrick skin types

Figure 13.1.1-1: Fitzpatrick Skin Type Chart

Type 1	Red & blonde hair, blue eyes, burns easily, never tans, freckles, very fair skin.	High risk for skin cancer, may scar if slow to heal.
Type 2	Fair sandy/red hair, green or blue eyes, burns easily, tans with difficulty, some freckles.	High risk for skin cancer, may pigment with trauma and may scar if slow to heal.
Type 3	Brown, fair, sandy hair; green, hazel, blue eyes. Slow to burn, will tan.	High risk for all pigmented skin conditions; moderate risk for skin cancer; higher potential for scarring.
Type 4	Dark brown hair; green, hazel, brown eyes. Slow to burntans easily.	High risk for trauma, heat & chemically caused pigmentation, and moderate risk for all other pigmented skin conditions. High risk for scarring.
Type 5	Dark and black hair; brown and dark brown eyes. May never burn.	Very high risk for trauma, heat & chemically caused pigmentation, and lower risk for solar pigmented skin conditions. High risk for scarring (keloid).
Type 6	Black hair, dark brown eyes. May never burn.	Very high risk for trauma, heat & chemically caused pigmentation, and lower risk for solar pigmented skin conditions. Very high risk for scarring (keloid).

13.1.3 Burn Chart

A replica of the following diagram will be used to depict the location and shape of the burn. It may be used as an aid to calculating BSA, if other methods are not available. (from Fenlon S, Nene S Contin Educ Anaesth Crit Care Pain 2007;7:76-80)

[figure not shown]

Figure 13.1.2-1: Lund and Browder Chart

Area	Age 0	1	5	10	15	Adult
A = half of head	91/2	81/2	61/2	5½	41/2	31/2
B = half of one thigh	2¾	31/4	4	41/2	41/2	4¾
C = half of one lower leg	21/2	21/2	2¾	3	31/4	31/2

13.1.4 Burn Wound Appearance

Exudate amount	□ copious
	□ large
	□ moderate
	□ small
	□ scant
	□ none
Exudate type	☐ foul purulent
	☐ fresh blood
	□ green
	□ sanguinous
	□ serosanguinous
	□ yellow
Odor	□ none
	□ mild
	□ strong
Presence of eschar	□ present
	□ not present
Presence of epithelial islands	□ present
	□ not present
Epithelialization of the burn wound	expressed as a percent of the burn wound area re-epithelialized
Burn wound closure	□ closed
	□ open
Peri-burn skin	□ cyanosis
	□ ecchymosis
	□ edema
	□ erythema
	□ intact
	□ maceration
	□ pallor
	\square rash – if present, complete rash evaluation per Appendix 18.1.4.

13.1.5 Rash Evaluation

Periwound rash	1 □ None
	2 ☐ Macular or multiforme
	3 □ Confluent erythema
	4 □ Papular or nodular
	5 □ Vesicular
	6 □ Pustular

13.1.6 Subject Scar Assessment Scale

No, not at all											Yes, very much
	1	2	3	4	5	6	7	8	9	10	
Was the scar painful during the last weeks?											-
Was the scar itching during the last weeks?											
Like normal skin											Worst Difference
	1	2	3	4	5	6	7	8	9	10	
Is the color of the scar different from your normal skin?											-
Is the pliability of the scar different from your normal skin?											
Is the thickness of the scar different from your normal skin?											
Is the scar surface more uneven than your normal skin?											
Best possible scar	1	2	3	4	5	6	7	8	9	10	Worst possible scar
What is your general impression of the scar at this moment?											-

13.1.7 Vancouver Scar Scale

1.	Vascularity	Normal	0
		Pink	1
		Red	2
		Purple	3
2.	Pigmentation	Normal	0
		Hypopigmentation	1
		Hyperpigmentation	2
3.	Pliability	Normal	0
		Supple	1
		Yielding	2
		Firm	3
		Ropes	4
		Contracture	5
4.	Height	Flat	0
		< 2 mm	1
		2-5 mm	2
		> 5 mm	3
